## 13 TRIAL DATA

### 13.1 Data to be collected

Data will be collected by members of the site research team with delegated responsibility from the PI. Data will be collected as reported by patients including the use of questionnaires, from patient notes and electronic medical records, and medical images collected during clinical care or the research procedures. Data will be collected at baseline, during the admission for the PCI procedure, at subsequent follow-up visits and at the time the research team are made aware of serious or non-serious adverse events.

Data fields to be collected will follow the list of schedule of assessments detailed in section 6.10. The primary outcome will be collected via the Kansas City Cardiomyopathy Questionnaire, a validated tool for assessing health status in patients with heart failure.

### 13.2 Electronic Case Report Form (eCRF)

Data will be collected via an Electronic Case Report Form (eCRF), managed by Sealed Envelope Ltd. and hosted by Rackspace. In accordance with GCP, the electronic data entry system will be validated and Working Procedure Documents covering its use will be drafted and maintained. All data entered into the eCRF will be pseudonymised, and identifiable data will not leave NHS trusts.

#### 13.2.1 eCRF access at site level

The eCRF will be accessed by users through a normal web browser. Each user will have their own individual account and secure password. Only personnel authorised by the LSHTM CTU will be granted access to the eCRF. Site staff will only be able to access data for participants recruited at their site. Direct access to the eCRF will be granted to authorised representatives from the Sponsor, host institution and the regulatory authorities to permit trial-related monitoring, audits and inspections. eCRFs should be completed within 2 weeks of each trial milestone where possible. Principal Investigators at each site have overall responsibility for the accuracy, completeness and legibility of the data entered onto the eCRF and associated reports.

### 13.3 Data security

Trial participants will be identified by a unique trial specific number and/or code in any database. The name and any other identifying detail will not be included in any trial data electronic file. Patient data will be kept confidential and managed in accordance with the Data Protection Act (2018), NHS Caldecott principles, the Research Governance Framework for Health and Social Care, and the conditions of Research Ethics Committee Approval. Personal patient data will be archived at the site after the end of trial.

### 13.4 Data management

The trial data manager will be responsible for checking the quality and validity of data and will raise queries with sites where statistical or qualitative monitoring identifies potential errors.

### 13.5 Personal Data Breaches

GDPR broadly defines personal data breaches as a security incident that has affected the confidentiality, integrity or availability of personal data. In short, there will be a personal data breach whenever any personal data are lost, destroyed, corrupted or disclosed; if someone accesses the data or passes it on without proper authorisation; or if the data are made unavailable, for example, when it has been encrypted by ransomware, or accidentally lost or destroyed.

Personal data breaches must be immediately reported to the Sponsor/data controllers and to the Data Protection Officer/IG Department of the site that incurred the breach. The following information must be provided to assess the full risk/impact of the breach: full details as to the nature of the breach, an indication as to the volume of material involved, and the sensitivity of the breach (and any timeframes that apply), steps that have been taken to mitigate the risk (trying to retrieve the data asking third parties to delete information that was sent to them in error).

Sites will additionally follow their Trust incident reporting mechanisms such as Datix and will document this within their TMF/ISFs in the form of a file note provided by the Sponsor with corrective and preventative measures addressed.

The Sponsor/data controller will determine whether the breach meets the definition of a serious breach and warrants reporting to the regulators including the ICO <https://ico.org.uk/for-organisations/report-a-breach/personal-data-breach-assessment>.

### **13.6 Data sharing**

Consent will be sought from participants for data sharing via the participant consent form at the time of consenting to the trial. All data sharing will be in accordance with this consent, the Data Protection Act 2018 and UK General Data Protection Regulation (GDPR). All identifiable data will be held at NHS sites and will not be shared with anyone else or outside of the UK.

At the end of the project, the pseudonymised data will be transferred from LSHTM to King's College London (KCL) for further analysis and long-term storage in the KCL Trusted Research Environment. This transfer will be in the form of a locked excel document via encrypted and secure data transfer. The data will be stored at KCL for a period of 20 years. The flow of data leaving NHS Trusts can be found in Appendix 2.

A pseudonymised dataset will be made publicly available 1 year after the end of the study in accordance with best practices in research data sharing. This database will have all identifiers removed (including dates and study numbers) but remains pseudonymised due to the size of the sample and possibility of unique combinations of characteristics within the dataset may allow identification of a participant.

## **14 STUDY WITHIN A TRIAL (SWAT)**

The REPRIEVED SWAT focusses on the under-representation of women and minoritised ethnic groups in interventional heart failure trials. The SWAT will take a mixed-methods approach to understanding the reasons for under-representation in these trials.

Qualitative work will include ten interviews with patients and care partners to explore their thoughts on recruitment and where hesitation or mistrust can lie. Two focus groups will also explore staff's perceptions and where they identify barriers before and after cultural safety training. The outcomes of these interviews and focus groups will be reported and will inform trial recruitment strategy.

Qualitative work during recruitment will involve analysis of ten recorded consent or information sessions to assess communication, barriers to participation and opportunities for improvement, as well as five patient reporter follow-up interviews. The learning from these interviews and recordings will be supplemented by quantitative monitoring of screening, recruitment and retention data monthly to measure the impact of interventions on the representation of under-served populations. The SWAT results will be published to share learning. The SWAT will be co-led by the one of the PPI Co-Applicants ([name]) and [name] with the support of the CI and CTU, to facilitate the

focus groups, recordings, interviews and provide expertise in qualitative research in under-served populations.

The interviews and focus groups will support the recruitment process. These will provide insights from patients and care partners to give us an idea of the landscape in terms of mistrust, trial hesitancy, and preferred communication methods. We will also develop insights from trial staff to give us an idea of potential gate keeping before it begins, training needs, and insights from their own experience of working directly with patients.

The analysis of recruitment consultations and monitoring of recruitment/retention data will allow us to proactively evaluate the recruitment and retention process in an ongoing and proactive manner rather than a reactive manner. The SWAT should provide quantitative evidence on the current success of recruitment, and the qualitative evidence on how to act and adjust the processes if recruitment is behind target.

## 15 MONITORING AND AUDITING

The Chief Investigator will be responsible for the ongoing management of the study, with the support of the LSHTM CTU.

The Sponsor will monitor and conduct audits on a selection of studies in its clinical research portfolio. Monitoring and auditing will be conducted in accordance with the UK Policy Framework for Health and Social Care and in accordance with the Sponsor's monitoring and audit procedures.

### 15.1 *Central statistical monitoring*

The primary method of data monitoring will be via central statistical monitoring. Site monitoring visits will not routinely be conducted but may be arranged if concerns regarding the integrity and quality of research data are raised either by the site, CTU or a trial committee.

The eCRF will form the primary record for the study at site level. Paper records are not required but may be used by sites to facilitate data entry. Integrity of the eCRF may be checked against source records during monitoring visits.

### 15.2 *Monitoring due to protocol non-compliance*

A monitoring visit may be required due to concerns about protocol non-compliance, such as to prevent serious breaches from reoccurring (further details can be found in the Protocol compliance WPD).

### 15.3 *Recording research conduct at site*

Sites are required to maintain up to date and detailed records of research conduct. These include but are not limited to the site file, delegation and training logs, records of adverse events and their reporting and any other records required by relevant regulatory bodies.

## 16 STATISTICAL CONSIDERATIONS

A detailed statistical analysis plan will be written and signed off prior to database lock and unblinding of trial data. For the KCCQ-OSS and CFR measures, differences in mean levels of the outcome measures between treatment groups at the relevant timepoints will be calculated, together with 95% confidence intervals, using a linear mixed model with treatment group, categorical treatment by timepoint interaction and baseline outcome measures included in the model (random intercept, unstructured correlation). It may be necessary to examine the measures for transformations to adhere to the assumptions of the linear mixed model or use bootstrapping techniques if a suitable

transformation cannot be found. For the primary analysis, any patient who dies will be excluded but as a sensitivity analysis a value of 0 will be imputed. All analyses will be on an intention-to-treat basis. Key secondary outcomes include all-cause death and/or hospitalisation for heart failure which will be assessed and compared between groups with hazard ratios using a Cox proportional hazards model. In addition risk differences will also be presented together with 95% confidence intervals at 6 months. The individual components of all-cause-death and hospitalisation for heart failure will also be analysed. In addition, groups will be compared using the unpaired win ratio method with a prespecified hierarchy of all-cause death, hospitalisation for heart failure and difference in KCCQ-OSS  $\geq 7$  between participants at six months. Sensitivity analyses will be reported excluding any participants who underwent emergency unblinding. Whilst the sample size will not permit definitive analyses based upon subgroups, hypothesis generating subgroup analyses will be performed to assess for differential treatment response based on age, sex and baseline NT-pro-BNP.

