#### Outcome measures:

- **Primary efficacy:** The primary efficacy outcome is the difference in KCCQ-OSS between treatment groups at 6-month follow-up. The Kansas City Cardiomyopathy Questionnaire (KCCQ) is the most widely used disease-specific tool for patient reported quality of life outcomes in heart failure, has been specifically validated in HFpEF and is the recommended tool for assessing functional and psychosocial outcomes in the International Consortium for Health Outcomes Measurement (ICHOM) standard outcome set for heart failure published in 2020.
- **Primary mechanistic:** The primary mechanistic outcome is the difference in CFR between treatment groups, after PCI has been performed in the PCI group. CFR is an independent predictor of future adverse cardiovascular events and allows us to determine the relationship between the severity of epicardial and microvascular disease and quality of life.
- **Secondary outcomes:** Key secondary outcomes include all-cause death and hospitalisation for heart failure. Further secondary outcomes include the efficacy of blinding (assessed using standard tools), the ICHOM standard outcome set for heart failure, individual components of the KCCQ (including total symptom score and clinical summary score), New York Heart Association (NYHA) functional class, difference in NT-pro-BNP at six months and difference in left ventricular ejection fraction (LVEF) and diastolic function (mitral E/e') at six months.
- **Secondary mechanistic:** Secondary mechanistic outcomes include change in invasively measured FFR, CFR and microvascular resistance from pre- to post-PCI in all target coronary arteries measured during the PCI procedure.

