### **16.1 Sample size calculations**

In pilot data from our REVIVED-BCIS2 trial (which has been selected as calculations can be performed using individual participant data and represents the only randomised comparison of PCI to medical treatment in a heart failure population), the baseline KCCQ-OSS was 60.9 with a between-group difference at six months of 6.5 (95% confidence interval 3.5 to 9.5) points. There was a high degree of correlation between baseline and six-month scores (correlation coefficient: 0.67). Though the standard distributions of scores at each timepoint were non-normally and widely distributed, the distribution of change in score from baseline to follow-up was close to normally distributed. Assuming similar baseline values, a standard deviation of KCCQ-OSS of 25, correlation coefficient of 0.6 and an alpha of 0.05, a total of 350 participants are required to have in excess of 85% power to detect a minimum clinically important difference (MCID) of 7 points, allowing for 10% withdrawals or losses to follow-up. If correlation were higher (0.65) a sample size of 350 participants will achieve in excess of 90% power for a difference of 7. If the standard deviation were increased (27), we would retain in excess of 80% power for a MCID of 7. The inclusion of a three month follow-up timepoint will enable repeated measures of KCCQ-OSS which will further increase power. A review of the sample size assumptions blinded to treatment allocation will be made after 1 year of recruitment to assess the correlation between baseline and follow up measures; consideration will be given to extending the sample size at this point if recruitment permits.

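### The primary KCCQ-OSS analysis drops every participant who dies, which conflicts with the intention-to-treat statement, compares survivors only and discards 3-month scores already observed

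*Protocol*

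**What the plan says.** The primary efficacy outcome is defined in the protocol's Section 5.1: "The primary efficacy outcome is the difference in KCCQ-OSS between treatment groups at 6-month follow-up". Section 16 analyses it "using a linear mixed model with treatment group, categorical treatment by timepoint interaction and baseline outcome measures included in the model". On deaths it says: "For the primary analysis, any patient who dies will be excluded but as a sensitivity analysis a value of 0 will be imputed". The sentence after that reads: "All analyses will be on an intention-to-treat basis".

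The trial schedule (Section 6.12) collects the KCCQ at baseline, at the procedural visit, and at 3 and 6 months. The procedural-visit score is taken before randomisation (Sections 6.5.2 and 6.10.2), so the 3-month score is the first one after it. Section 16.1 counts on that score: "The inclusion of a three month follow-up timepoint will enable repeated measures of KCCQ-OSS which will further increase power".

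Section 16 also plans a Cox model and 6-month risk differences for death and/or heart failure hospitalisation, separate analyses of each component, and a win ratio with all-cause death at the top of the hierarchy. For a participant who withdraws without stating a preference, Section 12.2 keeps the data collected up to that point.

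**The concern.** Death occurs after randomisation and treatment may change its frequency in either direction. The protocol accepts this: it makes all-cause death a key secondary outcome and lists cardiovascular procedures among the causes of cardiovascular death (Section 5.2). Removing the participants who die means that the groups compared are no longer the groups randomised. If those who die would have had poor health status, the arm that loses more of them looks better on the primary outcome.

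The rule also discards observed data. A mixed model can use a 3-month score when the 6-month score is missing, but here the whole participant is removed. Someone who withdraws at month 5 keeps the 3-month score by default; someone who dies at month 5 loses it. The protocol gives no reason for the difference.

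This is not a detail left to the statistical analysis plan. The protocol itself fixes the rule, so that plan must either repeat it or depart from it.

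**Working it through.** **1. The plan's own power.** Inputs from Section 16.1: 350 participants, a 7-point difference, "a standard deviation of KCCQ-OSS of 25, correlation coefficient of 0.6 and an alpha of 0.05", and an allowance described as "allowing for 10% withdrawals or losses to follow-up". Allocation is 1:1. Sidedness is not stated; two-sided is assumed.

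- Evaluable per arm: 350 × 0.9 / 2 = 157.5.
- Baseline-adjusted SD: 25 × √(1 − 0.6²) = 20.
- SE = 20 × √(2 / 157.5) = 2.254; 7 / 2.254 − 1.960 = 1.146; power = 87.4% (stated: more than 85%).
- With correlation 0.65: 90.5% (stated: more than 90%). With SD 27: 82.0% (stated: more than 80%).

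All three claims reproduce. The sample size is not in error.

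**2. Power if deaths come on top of the 10%.** With a proportion d of deaths, n per arm = 175 × (0.9 − d):

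| Additional deaths (assumed) | n per arm | Power (SD 25, correlation 0.6) |
|---|---|---|
| 0% | 157.5 | 87.4% |
| 2% | 154.0 | 86.7% |
| 5% | 148.75 | 85.5% |
| 8% | 143.5 | 84.3% |

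**3. Selection bias in the survivors-only comparison.** The protocol gives no 6-month death rate and no link between death and health status, so both are assumed. Let the log-odds of death rise by 1 for each SD (25 points) by which the 6-month score would have been lower.

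- When deaths are rare, those who die would then have scored about 25 points lower at 6 months. With correlation 0.6 their baseline is about 0.6 × 25 = 15 points lower.
- The model adjusts for baseline, which removes 0.6 × 15 = 9 points. The adjusted deficit is 25 − 9 = 16 points.
- Approximate bias = difference in death proportions × 16.

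A simulation with 2 million participants per arm and no true effect on KCCQ-OSS gave:

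| Assumed deaths, fewer v more | Hand formula | Simulated bias, towards the arm with more deaths |
|---|---|---|
| 2% v 2% | 0 | 0.0 |
| 1% v 3% | 0.02 × 16 = 0.32 | 0.3 |
| 2% v 5% | 0.03 × 16 = 0.48 | 0.45 |
| 3% v 8% | 0.05 × 16 = 0.80 | 0.73 |

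**4. The two sentences side by side.** One removes randomised participants because of an outcome after randomisation; the next claims intention-to-treat for every analysis. They agree only if intention-to-treat means no more than analysing people in the arm to which they were allocated. The protocol does not define it that way.

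**The case against.** The best defence is that quality of life does not exist after death, that a survivors-only contrast is declared openly, and that death is counted elsewhere: 0-imputation, Cox model, risk differences and win ratio. This stands as mitigation. Deaths are not ignored in the trial as a whole, but none of these analyses is the primary one, and none puts the discarded 3-month scores back into it.

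Three stronger readings are tempting, and the protocol does not support them.

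- **The rule has no time limit, so late deaths would also be removed.** Section 6.11 ends research follow-up once the six-month assessments are complete, and the primary outcome is fixed at 6 months. No later period is planned in which deaths would be collected.
- **The exclusions break the power claim.** The main statement, "a total of 350 participants are required to have in excess of 85% power", still holds with 5% deaths added to the full 10% loss. The 85% target needs 147 per arm, so it fails only when additional deaths exceed about (157.5 − 147) / 175 = 6%. The correlation-0.65 variant has little margin and slips to 89.9% with 2% deaths, but Section 16.1 does not say whether the 10% already covers deaths, and the calculation gives no credit for 3-month scores.
- **The gap to a death-as-0 result measures the bias.** It does not: scoring death as 0 answers a different question. If survivors differ by 7 points around the 60.9 mean quoted in Section 16.1, 3% deaths on PCI and 1% on placebo give 0.97 × 67.9 − 0.99 × 60.9 = 5.57. That is the planned sensitivity analysis at work. Likewise, applying the raw 25-point deficit overstates the bias because it ignores baseline adjustment.

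**Conclusion.** The concern holds. As written, the primary analysis is a survivors-only comparison, which conflicts with the intention-to-treat statement beside it and discards 3-month scores on which Section 16.1 relies.

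The likely size is modest: about 0 points if deaths are balanced, about 0.3 at 1% versus 3%, and 0.5 to 0.7 at 2% versus 5% or 3% versus 8%, on a 7-point target. These figures rest on assumed death rates and on the assumed link between death and health status. The direction is the awkward part, since the arm with more deaths benefits. The sample size needs no change on this account.

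**What to change.** Replace the exclusion sentence in Section 16 so that:

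- the primary mixed model includes all randomised participants, and those who die contribute every KCCQ-OSS score observed before death, with later scores treated as missing;
- the text states that participants who die before the 3-month visit have no score after randomisation, so the model cannot draw on them for the treatment contrast;
- those early deaths are counted by arm beside the primary result, and the already planned 0-imputation and win-ratio analyses are named as the ones that include them.

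The cost is a short amendment, with no new data, visits or participants. It should be made before anyone sees deaths by arm, since a rule chosen afterwards would not be credible. There is one small downside: the model implicitly projects scores beyond death. The retained 0-imputation analysis addresses that. The change does not remove selection through deaths before 3 months, which is why those deaths must be shown.

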### **16.1 Sample size calculations**

In pilot data from our REVIVED-BCIS2 trial (which has been selected as calculations can be performed using individual participant data and represents the only randomised comparison of PCI to medical treatment in a heart failure population), the baseline KCCQ-OSS was 60.9 with a between-group difference at six months of 6.5 (95% confidence interval 3.5 to 9.5) points. There was a high degree of correlation between baseline and six-month scores (correlation coefficient: 0.67). Though the standard distributions of scores at each timepoint were non-normally and widely distributed, the distribution of change in score from baseline to follow-up was close to normally distributed. Assuming similar baseline values, a standard deviation of KCCQ-OSS of 25, correlation coefficient of 0.6 and an alpha of 0.05, a total of 350 participants are required to have in excess of 85% power to detect a minimum clinically important difference (MCID) of 7 points, allowing for 10% withdrawals or losses to follow-up. If correlation were higher (0.65) a sample size of 350 participants will achieve in excess of 90% power for a difference of 7. If the standard deviation were increased (27), we would retain in excess of 80% power for a MCID of 7. The inclusion of a three month follow-up timepoint will enable repeated measures of KCCQ-OSS which will further increase power. A review of the sample size assumptions blinded to treatment allocation will be made after 1 year of recruitment to assess the correlation between baseline and follow up measures; consideration will be given to extending the sample size at this point if recruitment permits.

